**Table 2: █████ Parameters**

Parameter	Description	Analyte/Analysis Period	SAS Programming Notes
R █████/plasma	█████/plasma concentration ratios	Balovaptan, M2, M3	Calculated in SAS, using the plasma concentration from the corresponding timepoint of the █████ sample.

## 16.2 Pharmacokinetic Summaries

### 16.2.1 Pharmacokinetic Concentrations

Plasma concentrations for balovaptan, [C]-balovaptan, M2 and M3 below the quantifiable limit (BQL) will be set to ½ lower limit of quantification (LLOQ) in the computation of mean concentration values.

Descriptive statistics (number of subjects, arithmetic mean, geometric mean, SD, coefficient of variation, median, min, and max) will be used to summarize the plasma concentrations by treatment and analyte (i.e. balovaptan, [C]-balovaptan, M2 and M3) at each scheduled time point. If over ½ the subjects in a given cell have values BQL then the descriptive statistics will not be presented and will instead display as BQL for the mean and minimum. With the exception of maximum all other statistics will be missing.

Linear and semi-logarithmic plots of the geometric mean plasma concentration by scheduled sampling time will be provided by analyte, cohort, treatment and analysis day. Separate plots will be created by analyte and cohort (dose level), with the analysis days (SD and QD treatment) displayed in the same plot. These plots will show time in hours. The plots will match the summary table results and will not have an observation at a given time point if more than half of the subjects have values BQL. Geometric mean trough balovaptan, M2 and M3 concentrations (Period 2) will be plotted separately.

Combined individual (spaghetti) plots of the individual plasma balovaptan, [C]-balovaptan, M2 and M3 concentration versus actual sampling time will be provided by treatment and day. These plots will show time in hours.

Separate plots will be created for the individual plasma balovaptan, [C]-balovaptan, M2 and M3 profiles by treatment. These plots will show period 1 (single dose), day 1 and period 2 (multiple dose), day 14 per subject in the same plot. Individual plots will use the BQL handling procedure described below for "Pharmacokinetic Parameters".

Individual plasma concentration data will be presented together with descriptive statistics by analyte and treatment. ██████████ concentration data will be listed only.

### 16.2.2 Pharmacokinetic Parameters

Plasma PK parameters for balovaptan, [C]-balovaptan, M2 and M3, will be estimated using non-compartmental methods with WinNonlin®.

The plasma PK parameters will be estimated from the concentration-time profiles. In estimating the PK parameters, BQL values will be set to zero for the pre-dose PK sample, as well as for all other samples being BLQ and occurring before  $t_{max}$ . For subsequent time points, the result will be set to missing. Actual sampling times, rather than scheduled sampling times, will be used in all computations involving sampling times. If the actual time or dose time is missing, the scheduled time may be substituted in order to calculate the PK parameter.

Descriptive statistics (number of subjects, arithmetic mean, geometric mean, SD, geometric and arithmetic CV, median, min, and max) will be used to summarize the calculated PK parameters by treatment, day and analyte. For  $t_{max}$ , only median, min and max will be presented.

The points to be included in the  $\lambda z$  range will be determined by the pharmacokineticist after inspection of the semi-log concentration-time profiles. At least 3 points will be required to be used and the range should ideally be spread over a time interval representing at least 2 half-lives. The  $C_{max}$  data point will not be included.

Parameters based on  $R^2$  below 0.70 or %AUCextra above 20% will be flagged and excluded from descriptive statistics.

The ratio of geometric means from the microdose IV kinetics with that from the oral dose will be estimated using an analysis of variance (ANOVA) of the natural logarithm transformed clearance (CL and CL/F). A mixed model will be used, separately for the 2 cohorts with the 2 doses of 10mg and 50mg, and will include fixed effects for route (oral or iv) and for day (1 and 14) and a random effect for subject. From this model the least-squares means (LSMeans) for clearance (CL) of [C]-balovaptan iv and for CL/F of oral balovaptan will be presented. The ratios of the LSMeans for the comparison of CL to CL/F (IV/Oral) will be obtained by exponentiating the difference of the LSMeans on the log scale. A 90% confidence interval for the ratios of the treatment means will be calculated.

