3.3.2 Rationale for Balovaptan Dose and Schedule

A dose of 10 mg balovaptan has shown statistically significant changes in efficacy parameters in patients with ASD and is the current recommended Phase 3 dose.

In addition, a dose of 50 mg balovaptan will be studied as well to investigate any dose-dependent changes in oral bioavailability. In the MAD part of study BP25694, multiple doses of 52 mg QD in healthy subjects were well tolerated and resulted in a C_{max} of 484 ng/mL, [REDACTED]. Thus, a dose of 50 mg balovaptan QD is considered suitable to study dose-dependent changes in oral bioavailability.

Balovaptan is being developed for use in ASD, so it is expected that patients will need to take it for prolonged periods of time, likely for years or for life. Hence multiple dose testing is relevant from a clinical point of view. The multiple dose PK of balovaptan with 14 days of dosing was previously characterized in humans and was found to be time-dependent. Accumulation was observed with multiple dosing, and steady state of balovaptan was observed after approximately 7 days of dosing and after 10 days for M3. The plasma PK time course of M2 has not been closely studied but steady state has been demonstrated after 2 weeks of QD dosing with balovaptan 10 mg. Based on these observations, a dosing period of 14 days has been selected to ensure steady state plasma levels of balovaptan and its major metabolites M2 and M3 are reached and to maximize the possibility to observe any time-dependent changes in PK.

The microdose of [¹³C]-labeled balovaptan has been set to 0.1 mg; 0.1 mg is the maximum allowed IV microdose that can be administered without IV toxicity studies. Exposure after an 0.1-mg IV dose is covered by the existing nonclinical toxicity and PK

data. The t_{max} following oral dosing in the fasted state is expected to be approximately 1.5 hours postdose after a single dose and approximately 3 hours after multiple doses. To have the end of the infusion and the t_{max} of [^{13}C]-labeled balovaptan coincide with the t_{max} of the orally administered unlabeled balovaptan after a single dose, the 15-minute infusion of the microdose of [^{13}C]-labeled balovaptan will be started at 1.25 hours. For consistency the time of infusion is similar after the (last) multiple oral dose when due to accumulation plasma levels of balovaptan are predicted to not be lower than at t_{max} after the single dose.

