#### 5.2 Secondary Objectives

- To determine the absolute oral bioavailability of a single dose of 50 mg balovaptan.
- To determine the absolute oral bioavailability of balovaptan after once daily doses of 10 mg or 50 mg for 14 days.
- To characterize the dose- and time-dependency of the PK of oral balovaptan.
- To determine plasma concentrations of [C]-labeled balovaptan, balovaptan, and its metabolites M2, and M3, following a single oral dose of balovaptan 10 mg or 50 mg together with a slow intravenous (IV) infusion of a microdose of [C]-labeled balovaptan.
- To determine plasma concentrations of [C]-labeled balovaptan, balovaptan, and its metabolites M2, and M3, following once daily oral dosing of 10 mg or 50 mg once daily (QD) for 14 days together with a slow IV infusion of a microdose of [C]-labeled balovaptan after the last oral dose.
- To evaluate the safety and tolerability of balovaptan 10 mg QD and 50 mg QD.

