**Table 1: Plasma Parameters**

Parameter	Description	Analyte/Analysis Period	SAS Programming Notes
C max	Maximum plasma concentration. Observed peak analyte concentration obtained directly from the experimental data without interpolation, expressed in concentration units	All analytes	C max from WNL
C trough	Concentration at the end of the dosing interval (tau)	All analytes/ Period 2	The concentration at 24 h calculated in SAS
C last	Last measurable plasma concentration	All analytes	Calculated in SAS
t max	Time to maximum plasma concentration. First observed time to reach peak analyte concentration obtained directly from the experimental data without interpolation, expressed in time units.	All analytes	T max from WNL
AUC 0-last	Area under the concentration-time curve (time 0 to time of last quantifiable concentration).	All analytes/ Period 1	AUC last from WNL
AUC 0-inf	Area under the serum concentration-time curve (time 0 to infinity). Percent extrapolation less than or equal to 20% is required to obtain a reliable AUC inf .	All analytes/ Period 1	AUC INF_obs from WNL If AUC_%Extrap_obs >20% then parameter is not included
AUC 0-24h	Area under the serum concentration-time curve from time 0 to 24 hours post-dose	All analytes/ Period 1 and 2	AUC 0-24 from WNL where partial time =24, if missing for a subject then AUC at nominal time 24 hr from summary file is used for AUC 0-24
λ z	Terminal phase rate constant calculated by linear regression of the terminal log-linear portion of the concentration vs. time curve. Linear regression of at least three points and an adjusted R  greater than 0.70 are required to obtain a reliable λ z .	All analytes	Lambda_z from WNL If adjusted R  ≤ 0.7 the parameter is not estimated
t 1/2	Terminal phase half-life expressed in time units. Percent extrapolation <20% and adjusted R  greater than 0.7 is required to obtain a reliable t 1/2 .	All analytes	HL_Lambda_z from WNL If adjusted R  ≤ 0.7 the parameter is not estimated
t last	Time of last measurable plasma concentration	All analytes	Determined in SAS
R AUC	Accumulation ratio for AUC 0-24h	All analytes	Day 14 AUC 0-24h Period 2/ Day 1 AUC 0-24h Period 1 Calculated in SAS

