R Cmax	Accumulation ratio for C max	All analytes	Day 14 C max Period 2/ Day 1 C max Period 1 Calculated in SAS
R Ctrough	Accumulation ratio for C trough	All analytes	Day 14 C trough Period 2/ Day 1 C trough Period 1 (24 h sample on Day 2) Calculated in SAS
F	Absolute bioavailability (oral versus IV in %)	Balovaptan ([  C]- balovaptan)	Calculated in SAS as $F = \frac{AUC_{oral+DIV}}{AUC_{IV+Doral}} * 100$ AUC 0-inf of Balovaptan as AUC oral and AUC 0-inf of [  C]-Balovaptan as AUC IV
CL	Total body clearance (IV administration only) obtained by dividing the total dose of parent drug by its corresponding AUC 0-inf	[  C]-balovaptan	CL_obs from WNL
CL/f	Apparent total plasma clearance of drug after oral administration obtained by dividing the total dose of parent drug by its corresponding AUC 0-inf	balovaptan	CL_F_obs from WNL
V ss	Volume of distribution at steady state (IV administration only)	[  C]-balovaptan	V ss_obs from WNL

Note: AUCs will be calculated using linear up / log down, expressed in units of concentration x time.

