## Appendix 4: List of End of Text Outputs

List of End of Text Tables and Figures:		
Output	Title	Population Set
Section 14.1 – Disposition and Demographic Data		
Table 14.1.1	Summary of Subject Disposition	Safety
Table 14.1.2.1	Summary of Demographics	Safety
Table 14.1.2.2	Summary of Demographics (if applicable)	PK
Section 14.2 – Pharmacokinetic Data		
Table 14.2.1	Individual Values and Descriptive Statistics of Balovaptan and [  C]-Balovaptan Plasma Concentrations by Treatment, Analysis Day and Time-Point	PK
Table 14.2.2	Individual Values and Descriptive Statistics of Balovaptan and [  C]-Balovaptan Plasma PK Parameters by Treatment and Analysis Day	PK
Table 14.2.3	Individual Values and Descriptive Statistics of Balovaptan Metabolite (M2 and M3) Plasma Concentrations by Treatment, Analysis Day and Time-Point	PK
Table 14.2.4	Individual Values and Descriptive Statistics of Balovaptan Metabolite (M2 and M3) Plasma PK Parameters by Treatment and Analysis Day	PK
Table 14.2.5	Individual Values of Balovaptan and Balovaptan Metabolite (M2 and M3) Concentrations by Treatment, Analysis Day and Time-Point	PK
Table 14.2.6	Individual Values of Balovaptan and Balovaptan Metabolite (M2 and M3) Ratios	PK
Table 14.2.7	Ratio of geometric means of microdose IV kinetics (clearance) with that of oral dose	PK
Figure 14.2.8.1	Geometric Mean Balovaptan Plasma Concentrations versus Time (Linear and Semi-Logarithmic Scale) by Treatment and Analysis Day	PK
Figure 14.2.8.2	Geometric Mean [  C]-Balovaptan Plasma Concentrations versus Time (Linear and Semi-Logarithmic Scale) by Treatment and Analysis Day	PK
Figure 14.2.8.3	Geometric Mean Balovaptan Metabolite (M2 and M3) Plasma Concentrations versus Time (Linear and Semi-Logarithmic Scale) by Treatment and Analysis Day	PK
Figure 14.2.8.4	Geometric Mean Balovaptan and Balovaptan Metabolite (M2 and M3) Plasma Trough Concentrations (Linear and Semi-Logarithmic Scale) by Treatment	PK
Figure 14.2.9.1	Combined Individual Balovaptan Plasma Concentrations versus Time (Linear and Semi-Logarithmic Scale)	PK

Figure 14.2.9.2	Combined Individual [  C]-Balovaptan Plasma Concentrations versus Time (Linear and Semi-Logarithmic Scale)	PK
Figure 14.2.9.3	Combined Individual Balovaptan Metabolite (M2 and M3) Plasma Concentrations versus Time (Linear and Semi-Logarithmic Scale)	PK

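### SAP Table 1 and the Section 16.2.2 model conflict on Day 14: F, CL and CL/F rest on an AUC0-inf listed for Period 1 only, so a planned estimate is either missing or biased

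*SAP*

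**What the plan says.** **The model.** SAP 16.2.2: "A mixed model will be used, separately for the 2 cohorts with the 2 doses of 10mg and 50mg". The response is log clearance (CL for the labelled IV dose, CL/F for the oral dose). Fixed effects are route and day (1 and 14), and subject is random. There is no route-by-day term. The output is one IV/oral ratio with a 90% confidence interval, listed in SAP Appendix 4 as Table 14.2.7, "Ratio of geometric means of microdose IV kinetics (clearance) with that of oral dose".

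**The inputs.** SAP Table 1 defines CL/F as "Apparent total plasma clearance of drug after oral administration obtained by dividing the total dose of parent drug by its corresponding" AUC0-inf. CL is defined in the same way, and F is the dose-normalised ratio of the two AUC0-inf values. The AUC0-inf row is limited to Period 1 and adds: "Percent extrapolation less than or equal to 20% is required to obtain a reliable" value. AUC0-24 is listed for both periods but feeds none of F, CL or CL/F.

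**What Day 14 must deliver.** SAP 5.2 makes bioavailability after 14 days of dosing a secondary objective. SAP 5.2.1 names CL on Day 1 and Day 14 as an endpoint.

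**Dose.** SAP 5.2 also has the objective "To characterize the dose- and time-dependency of the PK of oral balovaptan". Protocol 3.3.2 justifies the higher dose because it "is considered suitable to study dose-dependent changes in oral bioavailability".

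**Descriptive output.** Geometric means, CVs and other statistics "will be used to summarize the calculated PK parameters by treatment, day and analyte". This covers F, without a confidence interval.

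**The concern.** The model asks for clearances on two days, but the parameter table supplies AUC0-inf for one period only. The programmer has to choose, and the choice changes what Table 14.2.7 estimates.

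If Day 14 is left out, a secondary objective and a named endpoint are not delivered. If Day 14 is filled in with AUC0-inf, the oral area after the fourteenth dose includes drug left from the previous thirteen, so oral CL/F is too low. An additive route-plus-day model passes that error into the only IV/oral ratio that carries an interval. For the 10 mg cohort, that ratio is the interval estimate closest to the primary objective, which concerns a single dose.

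In addition, the cohorts are analysed separately and no listed output compares them. The dose question is answered only by tables set side by side.

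**Working it through.** **1. Reproduce the plan's precision figure.** Inputs from Protocol 6.1: 6 subjects, 35% variability, 90% interval. With 35% used directly as the log-scale SD and a paired Day 1 contrast: exp(t(0.95; 5 df) × 0.35 × √(2/6)) = exp(2.015 × 0.35 × 0.577) = 1.50. At 30% and 40% the formula gives 1.42 and 1.59. All three match Protocol Table 4. The study was therefore sized for a Day 1 ratio.

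**2. What the additive model estimates.** On a simulated six-subject data set with a Day 1 route difference of 0.264 and a Day 14 difference of −0.293 (log scale):
- with all four cells present, the model's route contrast was −0.0145, the mean of the two differences;
- with the oral Day 14 cell removed, it was 0.264, the Day 1 difference.

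If Table 1 is followed literally, both Day 14 clearances are absent. The day effect then cannot be estimated, and the route contrast again rests on Day 1.

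**3. Carry-over if AUC0-inf is derived on Day 14.** At steady state, with linear one-compartment kinetics and rapid absorption, AUC0-inf/AUC0-24 = 1/(1 − exp(−24 ln2/h)). Protocol 1.2.1.1 gives h = 46 h after the last dose, so the ratio is 1/(1 − 0.697) = 3.30. Over an assumed range of 36 to 56 h it is 2.70 to 3.89. In the same model this ratio equals the accumulation ratio. The same protocol section reports accumulation of about 4-fold at 12 mg and 2-fold at 52 mg.

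If true F is equal on both days, averaging one correct day with one inflated day on the log scale inflates the ratio by the square root:

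| Source of carry-over | AUC0-inf/AUC0-24 | Inflation of day-averaged ratio |
|---|---|---|
| Accumulation at 52 mg | 2 | 1.41 |
| 46 h half-life | 3.30 | 1.82 |
| Accumulation at 12 mg | 4 | 2.00 |

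The [13C] area is not affected in this way. The previous labelled dose was 14 + 13 = 27 days earlier (648 h, about 14 half-lives of 46 h).

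**4. Interval factors for the IV/oral ratio at 35%.**

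| Analysis | Formula | n = 8 | n = 6 |
|---|---|---|---|
| Additive, averaged over days | exp(t(3n−2) × 0.35 × √(1/n)) | 1.24 | 1.28 |
| Route-by-day model, Day 1 | exp(t(3n−3) × 0.35 × √(2/n)) | 1.35 | 1.43 |
| Day 1 alone, paired | exp(t(n−1) × 0.35 × √(2/n)) | 1.39 | 1.50 |

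**5. A 50/10 ratio.** For F, with two independent cohorts and no between-subject spread in F: exp(t(2n−2) × 0.35 × √2 × √(2/n)) = 1.55 (n = 8) or 1.68 (n = 6). These are lower limits, since real spread in F would widen them. For Day 1 dose-normalised oral AUC, with the 42% between-subject variability of CL/F in Protocol 6.1 assumed for both doses: exp(t(2n−2) × 0.42 × √(2/n)) = 1.45 or 1.55.

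**6. Extrapolation of [13C].** Sampling ends 108 h after the oral dose (Protocol Appendix 2), which is 106.5 h after the infusion ends. With one compartment and 46 h, the extrapolated share is exp(−ln2 × 106.5/46) = 20.1%, against the 20% limit. It is 12.9% at 36 h and 26.8% at 56 h.

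**The case against.** **The primary estimate exists regardless.** F is calculated per subject and summarised by treatment and day, so the 10 mg single-dose geometric mean and CV will be reported. This stands. What the averaged reading removes is the model-based Day 1 interval, not the estimate.

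**A pharmacokineticist would use AUC0-24 at steady state.** Protocol 6.6 supports this: it ties AUC0-inf to a single dose and AUC0-24 to the dosing interval at steady state. But the SAP states that it supersedes the protocol's statistical considerations. Its CL/F row carries no period limit and gives only the AUC0-inf definition. The sensible choice is not written down.

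**The carry-over figure is model-bound.** This stands. The protocol describes time-dependent kinetics and more than dose-proportional exposure after single doses, so 1.82 should not be applied to both cohorts. The reported accumulation, itself translated through a linear model, suggests about 1.4 near 50 mg and 2.0 near 10 mg.

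**The 50/10 contrast is optional.** The aim is to characterise, the study is exploratory, no hypothesis is tested, and the cohorts are not randomised. A reader could build an interval from the planned geometric means and CVs. This makes it an analysis gap and not a contradiction. Even so, the SAP already reports a 90% interval for IV/oral. At n = 8 a ratio of 1.5 would carry an interval of about 0.97 to 2.32, which two means side by side do not show.

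**The extrapolation figure borrows an oral half-life.** This stands too. For a given terminal half-life, a distribution phase after the infusion would lower the extrapolated share. The result justifies reporting exclusions; it does not predict them.

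**Conclusion.** The plan is internally inconsistent on Day 14 and should be corrected before analysis. On the literal reading of Table 1, Day 14 F, CL and CL/F cannot be computed. On the other reading, the single IV/oral ratio per cohort is inflated about 1.4- to 2.0-fold (linear kinetics, steady state, equal true F on both days) and is no longer the Day 1 quantity behind the factor of 1.50.

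A reader might infer that the model at once lacks a usable Day 14 oral input and gives no Day 1 estimate. The documents do not support both together. Averaging over days requires Day 14 values to enter; if they are absent, the route contrast is the Day 1 difference. Nor is the gap only oral, because on the literal reading the labelled IV CL on Day 14 is missing as well.

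The missing 50/10 ratio with an interval is a real but secondary gap against a stated objective.

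**What to change.** 1. **Table 1.** Define Day 14 oral CL/F as dose divided by AUC0-24. Define Day 14 F as dose-normalised oral AUC0-24 over dose-normalised [13C] AUC0-inf, and state the steady-state assumption. Allow [13C] AUC0-inf and CL in Period 2.
2. **Model.** Add route-by-day and report the IV/oral ratio for each day, or estimate the 10 mg Day 1 ratio on its own as the primary estimate.
3. **Dose.** As estimation only, report F50/F10 and the 50/10 ratio of dose-normalised oral AUC (AUC0-inf on Day 1, AUC0-24 on Day 14), by day with 90% intervals. State that the cohorts are not randomised.
4. **Extrapolation.** Report how many [13C] profiles are excluded by the 20% rule, per cohort and day, with a sensitivity estimate that includes them.

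The cost is SAP wording, one model term, one secondary analysis and its table; no new data are needed. The downside is a wider interval for a Day 1 ratio than for a day-averaged one: at n = 8, a factor of 1.35 (route-by-day) or 1.39 (Day 1 alone) against 1.24. The 50/10 intervals will be wide and will not separate modest differences in F from none.

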6.6 PHARMACOKINETIC ANALYSES

Subjects will be excluded from the PK analysis population if they significantly violate the inclusion or exclusion criteria, deviate significantly from the protocol, or if data are unavailable or incomplete. Excluded cases will be documented together with the reason for exclusion. All decisions on exclusions from the analysis will be made prior to database closure.

Individual plasma ████████ concentrations at each sampling time point for balovaptan, M2, and M3, and individual plasma [¹³C]-labeled balovaptan concentrations will be presented by listings and descriptive summary statistics by treatment, including means, geometric means, ranges, standard deviations and coefficients of variation. Individual and mean concentration versus time will be plotted on semi-logarithmic scales.

The primary PK parameter is absolute bioavailability (F) for balovaptan following a single 10 mg dose.

The following plasma PK parameters will be estimated for balovaptan, M2, M3, and [¹³C]-labeled balovaptan:

- C_{max} : Maximum observed plasma concentration

- t_{\max} : Time to maximum observed plasma concentration
- $t_{1/2}$: Apparent terminal half-life
- AUC_{last} : Area under the plasma concentration-time curve from time zero to the last measurable plasma concentration time point (following a single oral dose)
- AUC_{inf} : Area under the plasma concentration-time curve from time zero extrapolated to infinity (following a single dose)
- AUC_{0-24} : Area under the plasma concentration-time curve over the dosing interval at steady state
- C_{last} : Last measurable plasma concentration
- C_{trough} : Concentration measured at the end of the dosing interval
- t_{last} : Time of last measurable plasma concentration
- λ_z : Terminal elimination rate constant
- R_{AUC} : Accumulation ratio for AUC_{τ} (Day 14 $AUC_{0-\tau}$ / Day 1 $AUC_{0-\tau}$)
- $R_{C_{\max}}$: Accumulation ratio for C_{\max} (Day 14 C_{\max} / Day 1 C_{\max})
- $R_{C_{\text{trough}}}$: Accumulation ratio for C_{trough} (Day 14 C_{trough} / Day 1 C_{trough})

The following plasma PK parameters will be estimated for the parent compound balovaptan:

- F : Absolute bioavailability
- CL : Total body clearance (IV administration only)
- V_{ss} : Volume of distribution

█ plasma concentration ratios will be calculated for balovaptan, M2, and M3, as applicable.

Additional PK parameters may be derived if deemed necessary.

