##### 5.2.1 Secondary Endpoints

- Absolute bioavailability (F) for balovaptan at the indicated dose level.

- Plasma concentrations and associated PK parameters for [C]-labeled balovaptan, balovaptan, and its metabolites M2, and M3, including but not limited to  $C_{max}$ ,  $t_{max}$ ,  $t_{1/2}$ ,  $AUC_{last}$ ,  $AUC_{inf}$ ,  $AUC_{0-24}$ ,  $C_{last}$ ,  $t_{last}$ ,  $\lambda_z$ , and (for [C]-parent only) CL on Day 1 and Day 14 and  $V_{ss}$  on Day 1 and Day 14.  
Any other parameter as appropriate (see Table 1)
- Adverse events (AEs), clinical laboratory values, vital signs, electrocardiogram (ECG), and physical examination.

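### Once Day 14 clearances enter the model, the only planned 90% interval pools Day 1 and Day 14 bioavailability: the primary single-dose 10 mg F then has no interval of its own, and the AUC behind Day 14 CL/F is contradictory

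*SAP*

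**What the plan says.** Protocol 6.6 names the target: "The primary PK parameter is absolute bioavailability (F) for balovaptan following a single 10 mg dose". F after 14 days of dosing is a separate secondary objective (SAP 5.2).

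The only interval in the analysis sections is in SAP 16.2.2, reported in Table 14.2.7. Log clearances (CL for the IV microdose, CL/F for the oral dose) go into a mixed model, fitted separately by cohort, that "will include fixed effects for route (oral or iv) and for day (1 and 14) and a random effect for subject". The least-squares means and their ratio are given by route. No route-by-day term, day-specific means or Day 1-only fit is named. F itself is also summarised by treatment and day, but the listed statistics include no confidence interval.

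On the AUC, the passages disagree:

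- The AUC0-inf row of SAP Table 1 is limited to "All analytes/ Period 1".
- The same table derives CL, CL/F and F from AUC0-inf. CL/F is the "Apparent total plasma clearance of drug after oral administration obtained by dividing the total dose of parent drug by its corresponding AUC" (0-inf), with no separate rule for Day 14.
- SAP 5.2.1 lists "CL on Day 1 and Day 14" among the endpoints for the labelled parent, and 16.2.2 uses day 14 as a model level.
- Protocol 6.6 ties AUCinf to single dosing, and defines AUC0-24 as "Area under the plasma concentration-time curve over the dosing interval at steady state". SAP Table 1 plans AUC0-24h for both periods but does not link it to CL/F or F.

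**The concern.** ln CL minus ln(CL/F) is ln F, so the IV/oral ratio is an estimate of F. An additive route + day model forces that ratio to be the same on both days. Protocol 1.3 says F is tested at steady state because the pharmacokinetics may depend on time. No document says F does change, but constancy over time is what the study sets out to examine, so it should not be built into the interval.

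What the ratio estimates depends on how the AUC conflict is resolved:

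- **A. Table 1 taken literally.** No Day 14 CL, CL/F or F exists. The day term has one level, the interval is the Day 1 interval, and the Day 14 F objective has no estimate.
- **B. Day 14 CL/F from AUC0-inf after the fourteenth dose.** That AUC includes drug left from earlier doses, so Day 14 F and the pooled ratio are inflated even if F is constant.
- **C. Day 14 CL/F from the dosing-interval AUC.** The ratio is a weighted geometric mean of the two days' F.

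Under B and C the interval that was meant to describe single-dose F describes something else.

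**Working it through.** **Inputs.** Variability 35%, 90% interval, 6 evaluable of 8 enrolled per cohort (protocol 6.1; SAP 6.1). Half-life about 46 h on Day 14, and accumulation about 4-fold at 12 mg and 2-fold at 52 mg (protocol 1.2.1.1). The ratio r = F_Day14/F_Day1 is not in the documents and is an assumption throughout.

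**1. The plan's own precision.** For a single-day paired comparison the factor is exp(t(0.95, n−1) × SD × √(2/n)), with the CV used directly as the log-scale SD. At n=6, t(0.95, 5) = 2.015:

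- SD 0.30: 1.418 (protocol Table 4: 1.42)
- SD 0.35: 1.503 (1.50)
- SD 0.40: 1.593 (1.59)

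All three rows reproduce, so the sizing is that of a Day 1 paired interval.

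**2. The SAP model.** Six subjects × 2 routes × 2 days = 24 observations; residual df = 24 − 6 − 2 = 16; t = 1.746. The factor exp(1.746 × SD × √(2/12)) is 1.238, 1.283 and 1.330 for the same SDs. At n=8 and SD 0.35, the pooled factor is 1.237 (22 df) against 1.393 for Day 1 alone.

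**3. What the pooled ratio estimates.** With complete data the additive route contrast is the mean of the two daily contrasts, so the ratio is √(F_Day1 × F_Day14) = F_Day1 × √r. A fitted example confirms it: daily contrasts of −0.713 and −0.143 average −0.428, and both the fixed-subject and the random-subject fit return −0.428.

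**4. Reading C.** √r gives 1.05, 1.12, 1.22 and 0.89 times Day 1 F at r = 1.1, 1.25, 1.5 and 0.8. Since F cannot exceed 1, r = 1.25 needs Day 1 F of at most 0.80, and r = 1.5 at most 0.67. Coverage of Day 1 F by the nominal 90% interval was simulated with 40,000 trials per cell, complete data and log-SD 0.35. The single-day variance of ln F was held at 2 × 0.35², and a share of it was either zero or placed in a stable subject-by-route effect:

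| Stable share | n | r=1 | r=1.1 | r=1.25 | r=1.5 |
|---|---|---|---|---|---|
| 0 | 6 | 90% | 88% | 82% | 65% |
| 0 | 8 | 90% | 88% | 78% | 56% |
| half | 6 | 78% | – | 70% | 57% |
| half | 8 | 78% | – | 68% | 50% |

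With a quarter of the variance stable, coverage at r=1 is 84 to 85%. The model has no subject-by-route term, so it treats the two days as independent information on F. The Day 1 paired t interval held 90% in every cell.

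**5. Reading B, true F unchanged.** Assuming one compartment and linear steady state, AUC0-inf/AUC0-24 after the last dose = 1/(1 − 2^(−24/46)) = 3.30, and √3.30 = 1.82. Under the same assumptions this quantity equals the accumulation ratio, so 2- and 4-fold accumulation give √2 = 1.41 and √4 = 2.00. Coverage of Day 1 F at 3.3-fold is about 6% (n=6) and 1% (n=8), with complete data.

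**The case against.** **The conclusion depends on the reading.** Under A the interval is the Day 1 one, with the planned factor of 1.50. That stands, but A leaves the Day 14 objective without an estimate and contradicts SAP 5.2.1 and 16.2.2. No reading leaves the plan intact.

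**Reading B has the least support.** SAP Table 1 and protocol 6.6 both tie AUC0-inf to single dosing. The SAP also drops AUC0-inf when extrapolation exceeds 20%. Day 14 oral sampling ends at 108 h, and 2^(−108/46) = 19.6%, so subjects with a half-life only slightly above 46 h would be lost, whereas the coverage figures assume complete data. This stands: the B figures show what Table 1's formula does if carried to Day 14, not what to expect. Nor is the B interval markedly tight. The day difference goes into the residual, and the typical factor at 3.3-fold is about 1.43 at n=6.

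**The size of r is assumed.** This also stands. At r = 1.1 with independent errors coverage is 88%, a small loss, and nothing in the documents supports a particular stable between-subject share.

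**Single-dose F is still reported.** Individual values, geometric mean and geometric CV are planned by treatment and day, and a reader could derive an interval from them. Protocol 6.6 promises none. But the sample size was justified by the width of that interval, and one derived afterwards is not pre-specified.

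**A route-by-day term would also do.** It gives a Day 1 contrast with factor about 1.43 at n=6 and 90% coverage with independent errors, but 86 to 89% when part of the variation is stable between subjects. It is workable, though less robust than the paired interval.

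**Conclusion.** The concern holds and should be fixed. If Day 14 clearances enter as SAP 16.2.2 states, the only planned 90% interval does not target the primary parameter. Under C it is off Day 1 F by a factor of √r and correct only if r = 1. Even then, coverage falls below 90% if part of the variation in F is stable within subjects. Under B it is off by roughly 1.4- to 2.0-fold with F unchanged. The pooled factor of 1.28, against 1.50 planned, comes from adding a second occasion and applies when F is similar on both days. Separately, and under any reading, Table 1 contradicts the Day 14 endpoints and objective.

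The consequences are limited. There is no hypothesis test or acceptance limit, and Day 1 F keeps its point estimate. What suffers is the accuracy of the reported interval. The size rests on assumed r, log-SD 0.35 and complete data; the B figures also need one compartment and linear steady state.

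**What to change.** In SAP 16.2.2, make the primary interval a Day 1-only paired analysis in the 10 mg cohort: ln F = ln CL − ln(CL/F) per subject, then the geometric mean with a 90% t interval on n−1 df. Do the same for 50 mg Day 1 as secondary. Show both as separate Day 1 rows in Table 14.2.7, without pooling days.

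Then reconcile SAP Table 1 with 5.2.1 and 16.2.2. Allow AUC0-inf in Period 2 for the single IV [13C] microdose only, and base Day 14 oral CL/F and F on the steady-state AUC0-24, which is already planned for Period 2. This follows protocol 6.6. Once that is settled, add Day 14 rows and the within-subject Day 14/Day 1 ratio of F with its 90% interval, read descriptively.

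The cost is a few sentences, corrected period and AUC entries in Table 1 and extra table rows; no new data. The Day 1 interval is wider than the pooled one (1.50 against 1.28 at n=6; 1.39 against 1.24 at n=8), but at n=6 it is exactly the stated precision. The Day 14/Day 1 ratio will be imprecise: exp(t(0.95, n−1) × 0.35 × √(4/n)) = 1.78 at n=6 and 1.60 at n=8, with independent errors. These factors assume no incomplete pairs. [13C] sampling ends 106.5 h after the infusion, and at a 46 h half-life extrapolation is 2^(−106.5/46) = 20.1%, right at the SAP's limit, so some pairs may be lost.
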